12 ADVERSE EVENT

12.1 Definition

An adverse event is defined as any untoward medical occurrence in a subject or clinical investigation subject administered a pharmaceutical or medical device product that does not necessarily have a causal relationship with this treatment. Adverse events include the following: all suspected adverse device or procedure reactions, occurrence of apparently unrelated illnesses (i.e., symptoms or diseases that were not present at study entry), worsening of a pre-existing illness (i.e., concurrent symptoms or diseases), injuries or accidents, or abnormalities in physiological or laboratory testing or physical examination findings that require clinical intervention or further investigation (beyond ordering a repeat confirmatory test). Throughout the study, subjects will be monitored for signs and symptoms of adverse events.

All adverse events reported during the study period will be recorded in detail in the subject's medical file and CRF.

12.2 Recording of Adverse Event

Subjects will be instructed by the PI to immediately report the occurrence of any adverse event. Each subject should be questioned at all visits whether any side effects or adverse events have occurred. All spontaneously volunteered, inquired, and observed adverse experiences will be recorded in detail.

12.3 Serious Adverse Events (SAE) and Unanticipated Adverse Device Effects

12.3.1 Definitions

Serious Adverse Events (SAEs) are defined as undesirable events experienced by a subject that suggest a significant hazard, contraindication, side effect, or precaution, whether or not considered to be device-related by the Investigator. An AE is defined as being serious if:

1. It is fatal or life threatening (life threatening means that in the opinion of the Investigator, the subject was at immediate risk of death from the adverse reaction).
2. It is permanently or temporarily disabling.
3. It requires inpatient or prolonged hospitalization.

4. Is a congenital anomaly/birth defect.

An unanticipated adverse device effect is defined as any serious adverse effect on health or safety, any life threatening problem, or death was not previously identified in nature, severity, or degree of incidence in the investigational plan or application (including a supplementary plan or application), or any other unanticipated serious problem associated with a device that relate to the rights, safety, or welfare of subjects.

12.3.2 Serious Adverse Event (SAE) Recording and Reporting

Any serious and/or unexpected adverse event that occurred while on study or one month after completion of study must be reported to DeNova Research via telephone and the Serious Adverse Event Report Form must be completed and faxed to DeNova Research and IRB within 24 hours of notification.

In addition, the local IRB (Institutional Review Board) or ERC (Ethics Review Committee) must be notified of all adverse events that are serious and/or unexpected.

All adverse events, including serious and unexpected events, must be recorded by the Investigator on the standard Adverse Event Report. This form will be included in the CRF. All Adverse Event Reports describing adverse events other than serious or unexpected adverse events will be inserted into the CRF. In addition, any serious and treatment-related unexpected adverse events must be reported to the local IRB (Institutional Review Board) within 5 business days of the event.

Subjects who have had a serious adverse event must be followed clinically until all parameters, including laboratory values, have either returned to normal, or are otherwise explained. If death was the outcome of the event on the initial Adverse Event Report, a Follow-up/Final Report, including autopsy report, when performed, must be completed.

13 QUALITY ASSURANCE

13.1 Institutional Review Board Approval

An IRB shall review and have authority to approve, require modifications in, or disapprove the investigation. Accordingly, this protocol, the informed consent document, and any relevant supporting information must be submitted to the IRB for review and receive approval prior to study initiation. Except in an emergency, any amendments to the protocol require approval by both Sponsor and the IRB prior to their implementation.

Additionally, the PI is responsible for providing the IRB with progress reports of the investigation at regular intervals (at least once per year), as well as with any other accurate, complete, and current information that the IRB may request concerning the investigation.

13.2 Informed Consent

Informed consent shall be documented by the use of a written consent form approved by the IRB and signed by the subject or the subject's legally authorized representative. A copy of the final, IRB-approved document must be provided for record-keeping purposes. Originals of the IRB-approved consent form and sign individual consent documents must be retained in the site's study files. Each subject must be provided with a copy of his/her signed consent form.

13.3 Study Monitoring

The PI will allow designees from the study sponsor to periodically audit all CRFs and corresponding source documents for each subjects, as well as, any data related to the study file. The monitoring visits provide for an opportunity to evaluate the progress of the study, to verify the accuracy and completeness of CRFs, to resolve any inconsistencies in the study records, and to assure that all protocol requirements, applicable regulations, and Investigator's obligations are being met. The PI must maintain source documents such as lab reports, photographs, history, and physical examination reports, etc., for possible review.

13.4 Modification of Protocol

If modification of the protocol is necessary, the modification must be confirmed with the IRB. No change to the protocol that significantly affects the safety, scope, or quality of the study may be implemented prior to written approval of the IRB. However, changes to the protocol may be made when necessary for the health of the subject. All modifications must be documented at the site. Moreover, if the study protocol is revised at any point during the study, IRB will be notified according to CRF 21 Part 812.

13.5 Departure from the Protocol

Minor deviations to the study protocol may be permitted if they will not increase the subject's risk or affect the validity of the study. All deviations must be documented at the study site.

When an emergency occurs that requires a departure from the protocol for an individual, a departure will be only for that subject. The PI in such an emergency will, if circumstances and time permit, contact the IRB prior to departing from the protocol. If this is not possible, such contact must be made as soon as possible, to allow an evaluation of the significance of such departure to the affected subject and to other subjects, and to permit a decision as to whether or not the subject (for whom the departure from the protocol was affected) is to continue in the study. The CRFs will completely describe the departure from the protocol and state the reasons for such departure. In addition, IRB will be notified in writing of such departure from protocol.

13.6 Confidentiality of Subject Records

The information obtained during the conduct of this study is confidential, and will be disclosed only to the Investigator and regulatory authorities as deemed necessary and/or as required by law. The PI must provide full disclosure of all study data and make study files available for inspection upon request by the IRB and/or relevant authorities including the study sponsor. Upon notice, the local authorizes may inspect and copy records that identify subjects through number and initial combinations. However, such copies have to be blinded (i.e., all personally indentifying data have to be blacked out) in order to prevent identification. The sponsor will be notified of any impending inspections relating to the study

13.7 Record Retention

The PI shall maintain accurate, complete, and current records relating to the participation in this study, including the following:

1. All correspondence including required reports.
2. Records of device shipment and disposition.
3. Signed Investigator Agreements.
4. The protocol and any protocol amendments.
5. Records concerning adverse events whether anticipated or not.
6. Documentation of each subject's case history and exposure to the device, including any CRFs, signed and dated consent forms, and any relevant medical records.
7. Any other records that the applicable authorities require to be maintained by regulation or by specific requirement for a particular device or category of devices.

The PI shall maintain all detailed essential documents for the duration of the investigation and for a period of at least 2 years since the formal discontinuation of clinical development of the investigational product, or 2 years after the last approval of any marketing application, or as required by the applicable regulatory requirements, whichever of them is a longer period.

13.8 Additional Principal Investigator Responsibilities

The PI is responsible for protecting the rights, safety, and welfare of subjects under his/her care. The PI is responsible for ensuring that the study is conducted according to the signed agreement with the investigational protocol, applicable regulations, and any condition of approval imposed by the IRB.

Premaxillary Injection
Version 2 July, 2017

14 Appendices

Appendix A: Photography Standardization

Appendix B: Diagram of planned measurements

Appendix A: Photo SOP**Photography and Poses**

- Use the grid feature on any of these viewers to ensure the Frankfort Plane (imaginary line from tragus to infraorbital rim) is parallel to the floor
- Stand approximately 1.5m from patient with the camera in a portrait position. The location will be marked on the floor of the photography studio.
- Ensure the patient has a relaxed expression and that their lips are closed and eyes are open for each photo.
- Give instructions like, “Slowly move you’re your chin down” or “Slowly turn your nose to the left” to achieve the desired poses listed below

Standard Poses ([contact] m)

1. Frontal
 - a. Make sure the patient doesn’t have their chin high or low by checking the Frankfort Plane. For this view, the line on the viewfinder should extend from the right tragus, across both infraorbital rims and across the left tragus. This should be parallel to the floor
2. Left Profile
 - a. For this view, ensure the patient is not rotated to the left or right (hint: look at the eyebrows to see how much of the glabella you see).
2. Right Profile
 - a. For this view, ensure the patient is not rotated to the left or right (hint: look at the eyebrows to see how much of the glabella you see).

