3 STUDY OBJECTIVES

The Primary Objective of this study is to determine the increase in nasal tip projection (measured by Goode's ratio) and the increase in upper lip projection (measured by the Z-angle) following perioral rejuvenation with premaxillary hyaluronic acid filler injections.

The Secondary Objective of this study is to assess the change in upper lip height by comparing the pre and post-treatment injection ratio of upper lip vermilion height to lower lip vermilion height.

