9 RESPONSE CRITERIA

9.1 Primary Variable Assessments

The primary assessment of this study is to determine the effect of premaxillary injection on nasal tip projection and upper lip projection for perioral rejuvenation. Efficacy of the injection on the subjects' 1-month post OCR with *Restylane® Defyne* will be done through comparative measurements taken on pre and post-treatment photographs.

Nasal tip projection will be assessed by Goode's ratio. The value is defined as nasal height over the nasal length. The nasal height is measured from the alar-facial groove to the tip-defining point and the nasal length is measured from the root of the nose, or nasion, to the tip-defining point. Upper lip projection will be measured by a method outlined by Merrifield in 1966. As described, a profile line is drawn tangent to the soft tissue chin and to the most anterior point of the upper lip. This line is then extended upward to the Frankfort horizontal plane. The angle at which these two lines intersect is called the Z angle. A change in the angle to a more acute value on postoperative photographs would indicate an increase in upper lip projection. This method was chosen because it is calculated independent of any postoperative nasal changes.

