11.3 Analysis Method

The PI's study coordinator will perform all statistical analyses. This is in an effort to avoid any potential bias that could be created by the treating physician participating in the analysis. Given that there is inherent variability even in standardized portrait photography, the decision was made to perform measurements based on facial landmarks and distance ratios. Statistical analysis will be conducted using a paired *t* test.

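### Appendix A does not fix bite or jaw position, although the primary Z-angle is drawn from the soft-tissue chin, which moves with the jaw

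*Combined protocol and SAP*

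**What the plan says.** Section 3 names upper lip projection, measured by the Z-angle, as a primary measure alongside nasal tip projection by Goode's ratio. Section 9.1 gives the construction: "a profile line is drawn tangent to the soft tissue chin and to the most anterior point of the upper lip", extended up to the Frankfort horizontal. It also gives the direction of benefit: "A change in the angle to a more acute value on postoperative photographs would indicate an increase in upper lip projection".

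Appendix A sets the conditions for the photographs:
- **Head pitch:** the Frankfort plane is levelled.
- **Rotation, in profile:** "ensure the patient is not rotated to the left or right".
- **Distance:** "Stand approximately 1.5m from patient with the camera in a portrait position", with the spot marked on the floor.
- **Face:** "Ensure the patient has a relaxed expression and that their lips are closed and eyes are open for each photo".

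Section 11.3 acknowledges that standardized photographs still vary, and answers that "the decision was made to perform measurements based on facial landmarks and distance ratios". The comparison is before against after treatment in 20 subjects, by paired t test, with no control group described (sections 5, 6 and 11.3). The text supplied for review says nothing about teeth, bite or jaw position. It gives no repeatability figure for the Z-angle, and the Appendix B diagram is not shown.

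**The concern.** Two soft-tissue points determine the profile line. One is the upper lip, which the treatment is meant to move. The other is the chin, which moves with the lower jaw. Levelling the Frankfort plane fixes the skull but not the jaw relative to it, and closed lips do not settle whether the teeth touch. A photographer can follow Appendix A exactly at both sessions and still record a different chin position.

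The safeguards elsewhere in the plan do not reach this. The Z-angle is an angle, not a distance ratio, so the section 11.3 remedy does not apply to it. The section 9.1 defence is that the angle does not depend on nasal change, which is a different matter. Excluding prior chin augmentation (section 6.2) does not control posture.

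Two things are at stake. Random jaw variation widens the interval around a primary estimate in a small study. A consistent difference in posture between sessions could not be told apart from a treatment effect, because there is no control group. A chin that sits further back at follow-up makes the angle more acute, which section 9.1 reads as benefit.

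**Working it through.** The plan states no SD, effect size, measurement error or sample-size derivation for the Z-angle, so there is no figure to reproduce. Of the inputs below, only n = 20 and the paired t test come from the documents. The rest are assumptions, including the two-sided 5% level, since the plan states neither alpha nor sidedness.

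**1. Chin shift to angle change**

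Let L be the vertical and h the horizontal distance from upper lip to chin. Then Z = arctan(L/h), so h = L/tan Z. Assume L = 30-50 mm and Z = 70-80 degrees. If the chin moves back by x and down by y, the fall in Z is Z - arctan((L + y)/(h + x)).

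| Chin movement | Fall in Z (degrees) |
|---|---|
| 0.25 mm back | 0.25-0.46 |
| 0.5 mm back | 0.50-0.92 |
| 1 mm back | 1.01-1.84 |
| 1 mm down, 0.5 mm back | 0.13-0.58 |
| 2 mm down, 1 mm back | 0.26-1.12 |

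Example (L = 30, Z = 80): h = 30/tan 80 = 5.29. With x = 1, arctan(30/6.29) = 78.16, a fall of 1.84. With y = 2 as well, arctan(32/6.29) = 78.88, a fall of 1.12.

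A full degree needs 0.54-0.99 mm of purely front-to-back movement. Downward movement alone raises Z, so moving down and back partly cancels.

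**2. Random variation: effect on the interval**

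This step uses the simpler approximation of a near-vertical profile line with L = 35-45 mm. Per-visit angle SD = arctan(s/L), where s is the per-visit SD of front-to-back chin position. The jaw part of the change has SD = √2 × arctan(s/L). It combines with the other variation as a sum of variances. Half-width = 2.093 × SD/√20 = 0.468 × SD. Assume the SD of change from all other sources is 2 degrees, which gives 0.468 × 2 = 0.94.

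- **s = 1 mm:** the per-visit SD is arctan(1/45) to arctan(1/35) = 1.27-1.64, and the jaw part of the change has SD 1.80-2.31. The total SD is √(4 + 1.80²) to √(4 + 2.31²) = 2.69-3.06, and the half-width is **1.26-1.43**, an increase of 0.32-0.50.
- **s = 0.5 mm:** the per-visit SD is 0.64-0.82, the jaw part has SD 0.90-1.16 and the total SD is 2.19-2.31. The half-width is **1.03-1.08**, an increase of 0.09-0.15.

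With the wider geometry of step 1 (1.01-1.84 degrees per mm), s = 1 mm gives √(4 + 2 × 1.01²) to √(4 + 2 × 1.84²) = 2.46-3.28 and a half-width of 1.15-1.54. If the other SD is 4 degrees, the half-width starts at 1.87, and s = 1 mm with L = 35-45 mm raises it to 2.05-2.16, an increase of 0.18-0.29.

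**3. Power**

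Take a per-photograph angle error of 1 degree and an other SD of 2. The total SD is √(4 + 2) = 2.45. By the noncentral t distribution, power for a true 1-degree change falls from about 56% to 41%, and for a 2-degree change from 98.9% to 93.3%.

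**4. Systematic shift**

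Suppose there is no true effect and jaw posture alone shifts the mean angle by 1 degree between sessions. The paired t test is then significant with probability 98.9%, 56%, 29% or 19% for a change SD of 1, 2, 3 or 4 degrees. These are conditional figures: nothing in the documents says that such a shift occurs.

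**The case against.** Appendix A is not silent on pose. It fixes pitch, rotation in profile, a marked distance, a relaxed expression, closed lips and open eyes, and section 5 asks for follow-up photographs in the same fashion as baseline. A relaxed face with closed lips already limits jaw posture. Part of the method is also out of sight: the Z-angle follows a cited method, and the Appendix B diagram is not shown. This stands as a limit on the point. It does not remove it, since nothing in the supplied text determines tooth contact.

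Four stronger readings are tempting, and the documents do not support them.

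- **That the SOP controls only the lips.** The list above shows otherwise. The gap is specific to the jaw.
- **That jaw position adds at least one degree of error.** No chin displacement is given anywhere. One degree needs about 0.5-1.0 mm of purely front-to-back movement. Parting the teeth may also lower the chin, and for the combined movements tabulated the change is mostly below one degree.
- **That the jaw term's own half-width is added to the interval.** At s = 1 mm the jaw term alone would give 0.468 × 1.80 to 0.468 × 2.31 = 0.84-1.08, but variances add and half-widths do not. The increase with an other SD of 2 is 0.32-0.50.
- **That the endpoint is biased.** Random variation leaves the mean change unbiased. The documents give no reason to expect a different bite at follow-up.

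**Conclusion.** The gap is real and minor. Appendix A leaves one of the two points defining a primary measure free to move, in a before-and-after study with no control group. On the assumed geometry the sensitivity is about 1.0-1.8 degrees per millimetre of purely front-to-back chin movement, and 0.26-1.12 degrees for 2 mm down with 1 mm back. What can be claimed is a possible loss of precision: a half-width of 1.26-1.43 instead of 0.94 degrees at a chin SD of 1 mm, and about 0.1 wider at 0.5 mm, with n = 20 and an assumed other SD of 2 degrees. If the other SD is larger, the added width is smaller. Bias is a possibility that the plan neither shows nor guards against. The case for acting rests on the remedy being simple and on jaw position not being correctable once the photographs are taken, rather than on a demonstrated large error.

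**What to change.** Add one line to Appendix A, in force before the first baseline photograph: for every pose at both sessions, the subject brings the back teeth lightly together, with the lips closed without strain, and the photographer checks this before each photograph by the same rule at baseline and at Visit 3. Light tooth contact is suggested because it is easy to instruct. What matters is that one jaw position is named and used at both sessions.

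Do not add a rule that compares the Visit 3 image with baseline and retakes it if the jaw looks different. It would have no stated tolerance and would apply discretionary selection to follow-up images only, in an open-label study, which could itself bias the result.

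The cost is one extra spoken instruction and check per photograph. No visit, measurement or analysis changes.

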Appendix B: Measurements
